
Study Procedures:

Patients will be randomly allocated into two equal groups.

Preoperative setting:

- Pre-operative assessment will be done by accurate history taking, full physical examination, laboratory and radiological investigations. including complete blood count (CBC), liver function test (LFT), kidney function test (KFT), prothrombin time (PT) and partial thromboplastin time (PTT) will be checked.
- All patient will be fasting for 8 hours pre operative.
- All patients will be informed about the study design, objectives and techniques.

- Informed consent will be signed by every patient prior to inclusion in the study.
- All patients will be educated about numeric pain scale score which 0 means no pain and 10 means worst imaginable pain.

Intraoperative setting:

- Standard perioperative monitoring will include pulse oximetry, electrocardiogram, end-tidal CO₂ measurement, inhaled volatile agent concentration and non-invasive blood pressure measurement.
- Baseline parameters such as oxygen saturation, systolic, diastolic and mean blood pressure, heart rate will be observed.
- Intravenous line will be inserted.
- For all patients, general anaesthesia will be induced by intravenous route using midazolam 0.04 mg/kg, fentanyl 1 µg/kg, propofol 2 mg/kg, atracurium 0.5 mg/kg.
- This will be followed by endotracheal intubation and mechanical ventilation. Maintenance of anaesthesia will be achieved by isoflurane 1.5% in oxygen and air (50:50) and atracurium 0.1 mg/kg every 20 minutes, so as to maintain end tidal CO₂ between 35 to 40 mm Hg.
- Intra operative heart rate and mean blood pressure will be recorded. Estimated blood loss will be determined.

Group A: (continuous caudal epidural with general anaesthesia “study group”)

- After induction of anaesthesia as mentioned above, patients will be located in the prone position for caudal epidural block. Sterile skin preparation and draping of the entire region will be completed in the standard fashion.

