- Fluoroscopy will be utilized and a lateral view will be obtained to demonstrate the anatomic boundaries of the sacral canal. With fluoroscopy, the caudal canal will appear as a translucent layer posterior to the sacral segments. The median sacral crest will be visualized as an opaque line posterior to the caudal canal. The sacral hiatus will be visualized as a translucent opening at the base of the caudal canal. The coccyx will be seen articulating with the inferior surface of the sacrum. A 17- or 18-gauge Tuohy-type needle will be inserted in the midline into the caudal canal. A feeling of a slight “snap” may be appreciated when the advancing needle pierces the sacrococcygeal ligament. Once the needle reaches the ventral wall of the sacral canal, it will be withdrawn and reoriented, directing it more cranially (by depressing the hub and advancing) for further insertion into the canal. The anteroposterior view will be used once the epidural needle is safely situated within the canal and the

epidural catheter will be advanced cephalad. In this projection, the intermediate sacral crests will appear as opaque vertical lines on either side of the midline. The sacral foramina will be visualized as translucent and nearly circular areas lateral to the intermediate sacral crests. Once the correct placement of the needle will be confirmed, a catheter will be inserted into the desired location while depth and position will be confirmed fluoroscopically.

- Before the local anaesthetic will be injected, careful aspiration or passive drainage is essential to exclude an unintentional intravascular or intrathecal needle location. An initial dose of 20 ml of 0.25% bupivacaine will be injected in the caudal canal in order to perform sensory block and spare motor power. Then a dose of 10 ml 0.25% bupivacaine will be injected through the epidural catheter every 1-hour intra operatively and at 0-hour and 1-hour post operative. Then the catheter will be removed 1 hour post operative.

Group B: (general anaesthesia “control group”)

- General anaesthesia will be induced as described above with administration of extra doses of fentanyl as needed according to hemodynamic changes suggesting pain sensation.

Post-operative setting:

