- After completion of surgery, the residual neuromuscular block will be reversed with injection of neostigmine 0.05 mg/kg and atropine 0.01 mg/kg. When patients become suitable for extubation, with stable hemodynamic and adequate muscle power, thorough oral and endotracheal suction followed by extubation will be done.
- Patients will be nursed in post anaesthesia care unit for monitoring of post operative vital signs and for post operative pain assessment by numeric pain scale score at 0-hour and management accordingly.
- Patients postoperative pain will be followed up at the ward at time interval 0, 1, 2, 4, 6 hours.
- Patients will undergo close monitoring for the first 6 hours after caudal injection for overdose or adverse reactions.
- The following factors will be assessed:
 - (1) Intra operative heart rate and blood pressure.
 - (2) Post operative pain assessment according to numeric pain scale score 1-10 as (0= no pain, 10 =worst imaginable pain) and hemodynamic parameters at 0, 1, 2, 4, 6 hours.
 - (3) Time to rescue analgesia (intravenous analgesia administered after

surgery) when the numeric pain scale score is 3 or higher. Patients with numeric pain scale score ≥ 3 at any point of time, will receive intravenous morphine 5mg.

- (4) Estimated blood loss and surgeon satisfaction of surgical field.
- (5) Total intra operative and post operative analgesia in both groups.
- (6) Common complications of caudal block in the postoperative period which include hypotension, bradycardia, lower limb numbness and urinary retention. These complications will be recorded and managed accordingly.

Measured outcomes:

Primary outcome:

- Determining the total amount of fentanyl that will be consumed as intra operative analgesia.

Secondary outcome:

- Determining the total amount of morphine that will be given as analgesia for the first 6 hours post operative.
- Analyzing the numeric pain scale score for the first 6 hours post operative.
- Detecting effect of continuous caudal epidural analgesia on intra operative and post operative hemodynamic changes.
- Identifying the time to the first demand for rescue analgesia.
- Justifying the use of continuous caudal epidural for analgesia in lumbar fixation surgeries.

Statistical analysis:

- Statistical analysis will be carried out using the statistical software SPSS program. Description of quantitative data as mean and standard deviation and qualitative data as number and percentage.

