- Comparison between the two groups will be done by using the Chi-square test, independent t-test or Mann-Whitney U-test according to the distribution of data. A p-value less than 0.05 will be considered statistically significant.

End point:

- Severe hemodynamic instability due to any surgical complication.
- Any surgical emergency that will need to reopen the patient in operating room.

- 6 hours post operative.

REFERENCES

- **Abdel Hady Sarah Mahmoud Farid Mahmoud, Ahmed Azza Youssef Ibrahim, Neamat-Allah Hatem Saaed Abdel Hamid, et al. (2022):** Combined caudal epidural with general anesthesia for lumbar discectomy. Ain Shams medical journal. 73(3): 695-704.
- **Benyahia Najoua Mokraï, Verster Ann, Saldien Vera, et al. (2015):** Regional anaesthesia and postoperative analgesia techniques for spine surgery – a review. Romanian Journal of Anaesthesia and Intensive Care. 22(1): 25-33.
- **El-Feky EM and Abd El Aziz AA. (2015):** Fentanyl, dexmedetomidine, dexamethasone as adjuvant to local anesthetics in caudal analgesia in pediatrics. Egypt J Anaesth. 31:175-80.
- **Eochagain Aisling Ni', Singleton Barry N., Moorthy Aneurin, Buggy Donal J. (2022):** Regional and neuraxial anaesthesia techniques for spinal surgery: a scoping review. British Journal of Anaesthesia. 129 (4): 598-611.

- **Hurley WR. (2010):** Acute postoperative pain. In: Miller RD, Eriksson LI, Fleisher LA, Wiener-Kronish JP, Young WL, editors. *Miller's Anesthesia*. 7th ed. Philadelphia: Churchill Livingstone. 2757-81.
- **Kao Sheng-Chin, Lin Chia-Shiang (2017):** Caudal Epidural Block: An Updated Review of Anatomy and Techniques. *BioMed Research International* 1:1-5.

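### Hypotension and bradycardia are counted as complications only after surgery, although the largest caudal dose and the hourly top-ups are given during it

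*Protocol*

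**What the plan says.** **Dosing.** Under Group A in Study Procedures, 20 ml of 0.25% bupivacaine is given into the caudal canal after induction. Further 10 ml doses of the same strength "will be injected through the epidural catheter every 1-hour intra operatively and at 0-hour and 1-hour post operative". The catheter is taken out at 1 hour post-operative.

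**Complications.** Factor (6) under Post-operative setting covers "Common complications of caudal block in the postoperative period which include hypotension, bradycardia, lower limb numbness and urinary retention", and adds that these are to be recorded and managed.

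**Close monitoring.** The same section states: "Patients will undergo close monitoring for the first 6 hours after caudal injection for overdose or adverse reactions". It does not say which of the several injections starts the clock.

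**Haemodynamic data.** Under Intraoperative setting, "Baseline parameters such as oxygen saturation, systolic, diastolic and mean blood pressure, heart rate will be observed" and "Intra operative heart rate and mean blood pressure will be recorded". Factor (1) assesses intra-operative heart rate and blood pressure. Factor (2) includes haemodynamic parameters at 0, 1, 2, 4 and 6 hours after surgery. Haemodynamic change in both periods is a secondary outcome.

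**Summaries and end of follow-up.** Statistical analysis specifies "Description of quantitative data as mean and standard deviation and qualitative data as number and percentage". End point lists "6 hours post operative" as the close of follow-up.

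**The concern.** The period over which complications are counted does not match the period over which the drug is given. Factor (6) does more than leave the period open: it names the postoperative period. Someone who follows it would not enter a pressure fall after the 20 ml dose, or after an hourly top-up, as a complication.

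The introduction undertakes to determine the possible complications of the technique and itself names hypotension among those of caudal anaesthesia. A table built on factor (6) would give the number of patients with hypotension or bradycardia after surgery only, and a reader could take it for the whole count.

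A smaller matter is that staff cannot tell from the close-monitoring sentence when the 6 hours end, because there are several injections.

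**Working it through.** The protocol states no figure on this point, so there is none to reproduce. The check sets the dosing times against the recording times.

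**Inputs from the protocol**
- First dose: 20 ml × 2.5 mg/ml = 50 mg, after induction.
- Each later dose: 10 ml × 2.5 mg/ml = 25 mg, hourly during surgery, then at 0 h and 1 h post-operative.
- Complication count: postoperative period.
- Close monitoring: 6 h from an unnamed caudal injection.
- End of follow-up: 6 h post-operative.

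**Assumption.** D is the number of hours from the first injection to the end of surgery. The protocol gives no value, so D = 2 to 6 is shown. Hourly doses fall at 1, …, D − 1 hours, and the dose at hour D is the 0-hour post-operative dose.

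**Step 1: drug given before the count opens**
- Before the end of surgery: 50 + 25(D − 1) mg.
- In total: 50 + 25(D − 1) + 2 × 25 mg.

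| D (h) | Before end of surgery (mg) | Total (mg) | Share |
|---|---|---|---|
| 2 | 75 | 125 | 60% |
| 3 | 100 | 150 | 67% |
| 4 | 125 | 175 | 71% |
| 5 | 150 | 200 | 75% |
| 6 | 175 | 225 | 78% |

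Across this range most of the drug, including the largest single dose, precedes the count.

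**Step 2: direction of the effect on the count.** The number of patients with an event after surgery cannot exceed the number with an event at any time from induction onward. The two are equal only if every patient with an intra-operative event also has a post-operative one. The restricted count is therefore either right or too low. The protocol gives no event rates, so the size of the shortfall cannot be calculated.

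**Step 3: the 6-hour watch**
- From the last dose, at 1 h post-operative: 1 + 6 = 7 h post-operative. Follow-up ends at 6 h, so 5 of the 6 hours lie inside it and 1 lies outside.
- From the first dose: the watch ends at 6 − D h post-operative, which is (6 − D) − 1 = 5 − D hours after the last dose. For D = 2, 3, 4, 5, 6 this is 3, 2, 1, 0 and −1 h.
- On either reading the scheduled haemodynamic checks continue to 6 h post-operative.

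**The case against.** The strongest reply is that intra-operative haemodynamics are already covered. Heart rate and mean pressure are recorded, assessed and compared between arms as a secondary outcome. Nothing forbids turning those readings into event counts: the analysis section provides numbers and percentages for qualitative data and a Chi-square test. Thresholds and table layouts commonly belong in a statistical analysis plan, which is not at hand. All of this stands, and it is why the point is small. It does not remove the point, because the recording period in factor (6) is set by the protocol, and set too narrowly.

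A second reply is that an intra-operative pressure fall cannot be attributed to the block in an individual patient, since everyone also receives propofol, fentanyl and isoflurane and loses blood. That is correct. It argues for reading the intra-operative rate as a difference between arms, not for leaving it out.

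Third, if the 6-hour watch starts at the first injection, it covers part or all of surgery. That softens the point, but monitoring a patient is not the same as counting an event.

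On the watch itself, the checks to 6 h post-operative limit the consequence to at most one hour, from 6 to 7 h. Nor does the end point say that clinical care stops there.

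**Conclusion.** The point holds as a low-severity improvement in safety reporting. Followed as written, the complication count omits intra-operative hypotension and bradycardia, and it understates the number of patients affected if any had such an event only during surgery. The 60% to 78% share of drug given before the count opens rests on the assumed D of 2 to 6 hours. That most dosing precedes the count holds throughout this range. The unnamed injection calls for a one-word clarification.

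Three stronger readings are tempting, and the protocol does not support them:
- *Intra-operative safety goes unobserved.* It does not: heart rate and mean pressure are recorded and compared in both arms.
- *A stated trial outcome fails.* A reader might point to "Justifying the use of continuous caudal epidural for analgesia in lumbar fixation surgeries", but that outcome concerns use for analgesia and is not a safety claim.
- *Patients go unwatched after the last dose.* Scheduled checks run to 6 h post-operative, 5 hours after that dose, on any reading.

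The primary outcome, power and sample size are untouched.

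**What to change.** **Factor (6).** In both arms, count hypotension and bradycardia from induction to the end of follow-up, from the heart rate and mean pressure already collected, at the same recording interval in each arm. Fix one threshold per event beforehand, in the protocol or the statistical analysis plan. For example: mean pressure more than 20% below baseline, and heart rate below 50 per minute. These values are proposed here and are not the protocol's; others will do if set in advance. Report intra- and post-operative numbers and percentages separately, and read the intra-operative rate as a between-arm comparison. Keep lower limb numbness and urinary retention as post-operative items.

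**Close-monitoring sentence.** Insert the word *last* before the reference to the caudal injection, and observe Group B to the same hour. Safety observation alone then runs to 7 h post-operative. The 6-hour pain and morphine outcomes stay as they are.

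**Cost.** A change of wording, one extra safety table, and at most one later observation per patient (2 × 30 = 60 in all).

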Official title

Comparative study of the effect of continuous caudal epidural with general anaesthesia versus general anaesthesia on intra operative and post operative analgesic requirements for lumbar fixation

DOCUMENT DATE:
APRIL 9, 2025

protocol

Comparative study of the effect of continuous caudal epidural with general anaesthesia versus general anaesthesia on intra operative and post operative analgesic requirements for lumbar fixation

Thesis

Submitted for Partial Fulfillment of M.D. Degree
in **Anaesthesiology, Intensive Care and Pain Management**

By

Postgraduate Student: [name]
Degree: M.B.B.CH., M.Sc., (Ain-Shams University)

Under Supervision of

DIRECTOR: [name] [name]

Academic Position: Professor of Anaesthesia, Intensive Care and Pain Management, Faculty of Medicine, Ain Shams University

CO-DIRECTOR: [name] [name]

Academic Position: Professor of Anaesthesia, Intensive Care and Pain Management, Faculty of Medicine, Ain Shams University

CO-DIRECTOR: [name] [name]

Academic Position: Lecturer of Anaesthesia, Intensive Care and Pain Management, Faculty of Medicine, Ain Shams University

CO-DIRECTOR: [name] [name]

Academic Position: Lecturer of Anaesthesia, Intensive Care and Pain Management, Faculty of Medicine, Ain Shams University

What is already known on this subject? AND What does this study add?

Caudal epidural anaesthesia has been used successfully in adult patients either as primarily sole anaesthetic technique or adjuncts to general anaesthesia to provide post operative analgesia. Pre-emptive caudal epidural is a proven technique for providing analgesia for spinal surgeries. Challenging aspect of spine surgery is to provide extended post operative analgesia.

This study is designed to evaluate the effectiveness of continuous caudal epidural for intra operative analgesia as alternative to opioid analgesia in general anaesthesia and reducing post operative opioid requirements to control post operative pain.

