1. INTRODUCTION/ REVIEW

Pain control during intra operative and post operative period for spine surgeries is crucial in patients as poor pain control may result in morbidity and mortality (**Fawzi & Almarakbi, 2012**). Severe acute pain prolongs hospital stay, delays mobilization and promotes subsequent chronic post-surgical pain (**Schug & Bruce, 2017**).

Whilst general anaesthesia is commonly used to undertake spine surgery, the use of neuraxial and peripheral regional anaesthesia techniques for intra operative and post operative analgesia is an evolving practice (**Gerbershagen et al., 2013**). Multimodal analgesia, including opioids, is used to limit pain after spinal surgery. Common adverse effects of opioids include nausea, constipation, ileus, delirium, itching, respiratory depression and respiratory tract infection (**Eochagain et al., 2022**).

Caudal anaesthesia was described in 1901 by two French physicians, Fernand Cathelin and Jean-Anthanase Sicard (**Waurick & Waurick, 2015**). The caudal epidural block was first introduced as a landmark-based, blind technique. Success rate in adults was 68–75% even in the experienced hands. Because of the inaccuracy of blind technique, some authors have recommended that caudal epidural injection is performed under fluoroscopic guidance (**Barham & Hilton, 2010**). Continuous caudal analgesia was first applied clinically, in 1941, being used to relieve pain for an

operation upon the lower extremity (**Kao & Lin, 2017**). Caudal epidural anaesthesia/analgesia is the most widely employed technique for various surgical procedures within the distribution of T10–S5 dermatome and it is easier to perform caudal procedure in the prone position (**Hurley, 2010**).

Caudal analgesia is a good, reliable and easy method to provide intra operative and post operative analgesia. However, the single shot caudal analgesia is short in duration, so the catheter injection may be used to prolong the analgesia time as continuous caudal epidural (**El-Feky & Abd El Aziz, 2015**).

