Caudal epidural analgesia, as pre-emptive analgesia, is an underutilized technique in adult patients undergoing lumbosacral spine surgeries. Caudal epidural block before surgery acts by blocking sensory input at the spinal cord level. Thus, pre-emptive analgesia has an important role in providing effective pain relief after lumbosacral spine surgeries (**Al Oweidi et al., 2010**). The combined caudal epidural analgesia with general anaesthesia is a proven technique in providing analgesia and managing post operative pain in lumbar spine procedures (**Lakshminarasimhaiah G et al., 2018**). It provides prolonged pain relief with adequate sensory block and limited motor blockade for early mobilization (**Nagappa et al., 2018**).

Among all available local anaesthetic bupivacaine is most commonly used. It produces a denser sensory block and enables better control of sensory and motor blockade while having the least incidence of an incomplete block (**Benyahia et al., 2015**).

Common complications associated with caudal anaesthesia include: Subdural, intravascular, or intraosseous injection, infection, hypotension, nerve roots injury, rectum perforation, hematoma formation, local anaesthetic toxicity, delayed respiratory depression, urinary retention, sacral osteomyelitis (**Wiegele et al., 2019**). A devastating complication of a caudal block is total spinal anaesthesia that can occur from an inadvertent dural puncture with subsequent intrathecal injection of local anaesthetic. Also, caudal epidural blocks have a higher incidence of local anaesthetic-related seizures (**Schug & Bruce, 2017**).

The overall benefit of intravenous analgesia versus caudal analgesia is still controversial, although many studies have shown that caudal epidural analgesia provides superior post operative analgesia compared to intravenous analgesia (**Kumar et al., 2017**).

In this clinical study, we will justify the current practice of combined continuous caudal epidural with general anaesthesia in adult patients undergoing lumbar fixation versus general anaesthesia. Furthermore, we will determine the analgesic

requirement, rescue analgesia, hemodynamic changes and possible complications with continuous caudal epidural analgesia.

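### One secondary outcome has no measurable content, and the adverse events listed for recording cover caudal complications but no opioid effects, so the trial cannot show whether opioid sparing reduces opioid harm

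*Protocol*

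**What the plan says.** **Purpose.** The opening summary says the study will evaluate the "effectiveness of continuous caudal epidural for intra operative analgesia as alternative to opioid analgesia in general anaesthesia". The Introduction states that "we will justify the current practice of combined continuous caudal epidural with general anaesthesia in adult patients undergoing lumbar fixation versus general anaesthesia", and promises to determine "rescue analgesia, hemodynamic changes and possible complications with continuous caudal epidural analgesia". Under Measured outcomes, the last secondary outcome is "Justifying the use of continuous caudal epidural for analgesia in lumbar fixation surgeries".

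**Opioid harm in the rationale.** The Introduction says: "Common adverse effects of opioids include nausea, constipation, ileus, delirium, itching, respiratory depression and respiratory tract infection".

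**Adverse events to be recorded.** Under Post-operative setting, item (6) of the assessed factors reads "Common complications of caudal block in the postoperative period which include hypotension, bradycardia, lower limb numbness and urinary retention". The same section says "Patients will undergo close monitoring for the first 6 hours after caudal injection for overdose or adverse reactions". Complications appear in neither the primary nor the secondary outcome list.

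**Opioid exposure.** Every patient receives fentanyl at induction (Intraoperative setting). Group B also has "administration of extra doses of fentanyl as needed according to hemodynamic changes suggesting pain sensation". Morphine is given after surgery when the pain score reaches the rescue threshold, with no restriction to one group.

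**The concern.** An outcome has to be something that can be observed and compared. Justifying a technique is a conclusion that a reader might draw from outcomes. Nothing in the protocol says which data would support that conclusion or count against it.

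The data that would bear on it are incomplete on one side. Part of the argument is that opioids cause adverse effects and that caudal analgesia reduces opioid use. The trial measures the reduction in use but none of the adverse effects. On the caudal side it lists complications, under a label and a monitoring clock that belong to Group A.

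Two things are at stake. A reduction in opioid-related harm, if there is one, would go unrecorded. And if staff read item (6) as applying only to patients who had a block, the complication counts would have no comparable counts in Group B. A later analysis plan can repair neither, because what was not recorded at the bedside cannot be analysed.

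**Working it through.** **1. The sample-size statement.** It concerns intraoperative fentanyl only. Inputs from Sample size justification: means 186.5 and 106 µg, SDs 21.6 and 16.4 µg, 30 per group, alpha 0.05 (taken as two-sided).
- Difference = 186.5 − 106 = 80.5 µg.
- Pooled SD = √((21.6² + 16.4²)/2) = 19.18 µg.
- Standardised difference = 80.5/19.18 = 4.20.
- Power at 30 per group is about 100% (noncentral t; already about 96% at 3 per group).

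The stated power above 90% is therefore correct. It says nothing about adverse events.

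**2. The opioid effects named, set against what is recorded.**

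| Effect named in the Introduction | Among assessed factors (1)–(6) or outcomes? | Plausibly seen within 6 h? |
|---|---|---|
| Nausea | No | Yes |
| Itching | No | Yes |
| Respiratory depression | No (vital signs are monitored, but no such event is defined or listed) | Yes |
| Delirium | No | Uncertain; early hours follow midazolam and isoflurane in all patients |
| Constipation | No | Hardly |
| Ileus | No | Hardly |
| Respiratory tract infection | No | Hardly |

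Count: 0 of 7 listed for recording. Follow-up ends at 6 h (End point), so only the short-onset effects are worth adding.

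**3. What the caudal list can be compared with.** Item (6) names four events. Three of them (hypotension, bradycardia, urinary retention) can occur without a caudal block. The item gives no time points and does not mention Group B. The adverse-reaction monitoring runs for 6 h from a caudal injection. Group A has several injections, before, during and after surgery, and the protocol does not say which one starts the clock. Group B has none. Pain scores and haemodynamics, by contrast, have fixed times of 0, 1, 2, 4 and 6 h after surgery.

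**4. What added items could show with 30 per group.** The documents give no event rates, so these are assumed. Power = Φ((d − 1.96·SE₀)/SE₁), with d = p₁ − p₂, p̄ = (p₁ + p₂)/2, SE₀ = √(2p̄(1 − p̄)/30) and SE₁ = √((p₁(1 − p₁) + p₂(1 − p₂))/30).
- 40% v 20%: SE₀ = √(2 × 0.30 × 0.70/30) = 0.1183; SE₁ = √((0.24 + 0.16)/30) = 0.1155; (0.20 − 0.2319)/0.1155 = −0.276; power 39%.
- 30% v 10%: SE₀ = √(2 × 0.20 × 0.80/30) = 0.1033; SE₁ = √((0.21 + 0.09)/30) = 0.1000; (0.20 − 0.2024)/0.1000 = −0.024; power 49%.
- 50% v 20%: SE₀ = √(2 × 0.35 × 0.65/30) = 0.1232; SE₁ = √((0.25 + 0.16)/30) = 0.1169; (0.30 − 0.2414)/0.1169 = 0.501; power 69%.

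For a rare event, none seen in 30 patients still leaves a one-sided 95% upper limit of 1 − 0.05^(1/30) = 9.5%. Over this range the added items can describe but cannot be expected to settle a comparison.

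**The case against.** The strongest reply is that this is a choice of endpoints. The Aim/Objectives section is limited to analgesic requirements, blood pressure, heart rate and pain scores, and it claims no comparison of harms. Opioid adverse effects take one sentence of the Introduction, which also stresses the consequences of poor pain control. The complications promised there are those of the caudal technique, and item (6) delivers them. The trial also measures direct patient benefit through pain scores and time to rescue.

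Much of this stands. Opioid harm is only one strand of the rationale, and nothing in the primary comparison is miscalculated or undermined.

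Two stronger readings are tempting, and the protocol supports neither:
- A reader might infer that the only harms the trial can detect are those of the caudal arm. Haemodynamics are followed after surgery without restriction to one group, so hypotension or bradycardia in Group B would be visible. Most of the other assessed factors do not name the groups either, so the silence in item (6) does not prove that Group B is left out. It leaves the matter open.
- A reader might infer that the wording of the outcome ensures a favourable result. The wording presumes a conclusion, but it determines no data. The uneven recording works, if anything, against the caudal arm: its complications are listed, while any reduction in opioid effects goes uncounted.

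What the reply does not answer is that an item without a variable stands among the measured outcomes, and that whether opioid sparing spares patients opioid effects is left unobserved.

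**Conclusion.** The point holds as an inexpensive improvement. It does not threaten the main result. One secondary outcome cannot be measured as written. None of the seven opioid effects that the protocol names is listed for recording, although opioids are given in both groups. Whether the four caudal complications are collected in Group B is not stated, so between-group comparability of those counts is uncertain.

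The comparisons of fentanyl and morphine consumption, pain scores, time to rescue and haemodynamics stand as planned. The conclusion rests on the listed factors and outcomes being the full set of adverse events to be collected. It depends on no event rate; the assumed rates bear only on how precise the added items would be.

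**What to change.** Replace the last secondary outcome with: number of patients in each group with any of the item (6) complications, and number with nausea, itching or respiratory depression, from 0 to 6 h postoperatively.

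- State that all these items are recorded yes/no in both groups at the existing 0, 1, 2, 4 and 6 h assessments, timed from the end of surgery in both.
- Have the investigators write down, before recruitment, how respiratory depression will be recognised.
- Leave out constipation, ileus and respiratory infection, which a 6 h window can hardly show. Delirium can be left to the investigators' judgement.
- Report counts and percentages by group with confidence intervals, as descriptive results without a claim of power.

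The cost is three extra yes/no items at assessments already planned and one reworded outcome. No visit, treatment or sample-size change is needed. The downside is slightly more data entry and comparisons that will be imprecise, so the absence of a clear difference should not be read as equivalence.
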